## 7.4 Multivariate Analysis

- **Binary logistic regression** to predict CIN occurrence, adjusted for covariates.

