### **1. Scientific Background.**

Contrast-induced nephropathy (CIN) is a frequent cause of acute kidney injury (AKI), particularly among hospitalized patients with diabetes mellitus. Individuals with diabetes are especially vulnerable due to metabolic disturbances, oxidative stress, and endothelial dysfunction, which heighten the risk of CIN following contrast exposure. Mechanistically, CIN is driven by reactive oxygen species (ROS), impaired nitric oxide (NO) bioavailability, and inflammatory processes (Tumlin et al., 2002; Heyman et al., 2008).

Remote ischemic preconditioning (RIPC)—a procedure involving brief episodes of non-lethal ischemia and reperfusion applied to a limb—has emerged as a potential non-invasive strategy to mitigate ischemia-reperfusion injury. Preclinical and clinical studies suggest that RIPC activates endogenous protective pathways, including the induction of heme oxygenase-1 (HO-1), modulation of NO signaling, activation of K+-ATP channels, and reduction of systemic inflammation (Zarbock et al., 2015; Er et al., 2012).

However, the efficacy of RIPC in diabetic populations remains controversial. Experimental data indicate that diabetes may interfere with key molecular signaling pathways responsible for RIPC-mediated protection. Impaired humoral signaling, autonomic dysfunction, increased oxidative stress, and diabetic neuropathy have all been implicated as potential mechanisms of attenuation (Li et al., 2010; Hausenloy et al., 2013). Approximately 20–50% of individuals with diabetes mellitus develop peripheral neuropathy, which may compromise neurogenic components of RIPC signaling (Pop-Busui et al., 2017).

Despite these concerns, some clinical trials have reported preserved protective responses in diabetic patients, particularly in the context of contrast administration. For instance, the RenPro Trial found that RIPC significantly reduced the incidence of CIN in both diabetic and non-diabetic populations (Er et al., 2012). These contradictory results may

reflect differences in glycemic control, duration of diabetes, antidiabetic pharmacotherapy, and the presence of comorbidities.

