### Secondary Objectives

- To assess HO-1 levels and other oxidative stress markers (malondialdehyde (MDA) before and after RIPC.
- To identify predictors of RIPC failure.
- To evaluate ICU/hospital stay duration, clinical status and survival at discharge.

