## 3. Study Design

- **Type:** Randomized, parallel-group clinical trial.
- **Setting:** ICU, Hospital General Universitario Santa Lucía, Cartagena (Murcia, Spain)
- **Randomization method:** Based on sealed envelopes, using block randomization into two groups: **RIPC** and non- **RIPC**.
- **Groups:**
  - **Intervention Group:** RIPC + hydration.
  - **Control Group:** Hydration only.
- **Planned sample Size:** The sample size was determined based on data from the ARIAM registry, a Spanish national database focused on patients with acute coronary syndrome (ACS) admitted to intensive care units. According to ARIAM estimates, approximately 35–40 patients per year would meet the eligibility criteria for recruitment. It was therefore decided that the sample size would be defined by the number of patients admitted to our department with the specified characteristics during a fixed time period, establishing a convenience sampling strategy over a two-year period.
- **Actual enrolled patients:** 71.
- **Analysis population:** Both Intention-to-Treat (ITT) and Per Protocol (PP).

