## 7.10 Significance Threshold

- All tests two-sided
- $p < 0.05$  considered statistically significant

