## 9. Study Limitations and Early Termination

Data collection was conducted over a three-years period. The final patient was enrolled and data collection for all primary and secondary outcomes, as well as adverse event monitoring, was completed in January 2017. Due to multiple logistical and operational constraints, no further patients were included after that date. Subsequently, with the emergence of the COVID-19 pandemic in December 2019, further recruitment was permanently halted. Additionally, preliminary analyses revealed that the primary outcome—the incidence of contrast-induced nephropathy (CIN) following remote ischemic preconditioning (RIPC)—did not show statistically significant differences between the intervention and control groups. These findings, combined with logistical constraints, led to the decision to halt the study before reaching the originally planned sample size. Thus, only 71 patients were enrolled—below the planned sample size. The reduced statistical power and lack of effect signal were key reasons for early termination.

**Note:** The study was not prospectively registered in a clinical trial database prior to patient enrollment. At the time of trial initiation, Spain did not have a clearly defined legal or regulatory framework mandating prospective registration for investigator-initiated interventional studies of this nature.

While Spain's Biomedical Research Law (Law 14/2007) established ethical principles and data protection standards, it did not impose a legal obligation to register non-pharmacological trials in platforms such as ClinicalTrials.gov or EudraCT. Furthermore, the regulatory provisions introduced by Royal Decree 1090/2015—which require prospective registration—apply specifically to clinical trials involving medicinal products and did not extend to procedural interventions such as remote ischemic preconditioning (RIPC). This regulatory gap, coupled with the academic nature of the study and its non-commercial scope, contributed to the lack of prospective registration.

This limitation is acknowledged and must be considered when interpreting results and assessing risk of reporting bias. The available data were analyzed and will be presented with full transparency regarding these limitations.

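### Section 7.4 plans covariate-adjusted logistic regression for CIN in 71 patients with no sparse-event method; if events are few, the fit can be unstable and the adjusted odds ratios imprecise or exaggerated

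*Combined protocol and SAP*

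**What the plan says.** Section 7.4 is a single line: binary logistic regression "to predict CIN occurrence, adjusted for covariates". It names no covariates, gives no number of them, does not choose between a Wald and a likelihood-ratio test, and does not say what happens if the model fails to converge. Section 7.5 checks only normality and equal variances, neither of which bears on sparse events. Section 7.9 names SPSS v25.0, and no penalised or exact method appears anywhere.

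This is the only multivariable model for CIN. It is also the only evident tool for the secondary objective "To identify predictors of RIPC failure". Section 1 suggests which covariates might be of interest: besides neuropathy, it says that conflicting earlier results may "reflect differences in glycemic control, duration of diabetes, antidiabetic pharmacotherapy, and the presence of comorbidities". Section 9 reports that "only 71 patients were enrolled". Section 7.2 gives a chi-square test for qualitative comparisons, which covers the unadjusted comparison of CIN between arms.

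**The concern.** Maximum-likelihood logistic regression relies on large-sample theory in the number of events, not the number of patients. With few events per model term, three things can go wrong. A covariate pattern can separate events from non-events, so that a fitted odds ratio runs to zero or infinity. The finite odds ratios that remain tend to lie too far from 1. The Wald and likelihood-ratio tests can disagree, and the plan does not say which would be reported.

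At stake are the adjusted RIPC odds ratio and any statement about predictors. If the fit fails, the plan has no rule for what to do next. Any covariate dropped at that point would be dropped after seeing the data, in a trial that was not prospectively registered and whose CIN comparison had already been examined (section 9).

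**Working it through.** The plan gives no event, power or precision figure to reproduce.

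**Inputs from the documents.** 71 patients (sections 3 and 9); two groups, "using block randomization into two groups" (section 3), ratio not stated; "All tests two-sided" at 0.05 (section 7.10).

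**Assumed inputs.** Arms of 36 and 35; control CIN risk 10–20%; arm plus five covariates (two continuous, three binary with prevalence 20–40%); covariate odds ratios between 1.0 and 1.5; maximum likelihood as the estimator.

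**Step 1: expected events and events per term.**
- No effect: 71 × 0.10 = 7.1 to 71 × 0.20 = 14.2 events.
- True odds ratio 0.5, control risk 10%: odds 0.111 × 0.5 = 0.0556, so risk 0.0556/1.0556 = 5.3%. Events: 35 × 0.10 + 36 × 0.053 = 5.4.
- True odds ratio 0.5, control risk 20%: odds 0.25 × 0.5 = 0.125, so risk 0.125/1.125 = 11.1%. Events: 35 × 0.20 + 36 × 0.111 = 11.0.
- Six terms (arm plus five): 5.4/6 = 0.9 to 14.2/6 = 2.4 events per term.

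Full planned recruitment would barely change this. Section 3 expects "approximately 35–40 patients per year would meet the eligibility criteria for recruitment" over two years, so 70 to 80 patients; 80 patients give 8 to 16 events.

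**Step 2: how often some coefficient has no finite estimate.** Separation was detected by linear programming in three simulations of this design (A: 1,200 trials per setting; B: 700; C: 800).

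| Control risk | 10% | 15% | 20% |
|---|---|---|---|
| No effect, any coefficient, A | 33% | 15% | 6% |
| No effect, any coefficient, B | 27% | 11% | 3% |
| No effect, any coefficient, C | 24% | 8% | 2% |
| No effect, RIPC itself, B | 5% | 0.4% | 0% |
| No effect, RIPC itself, C | 3.9% | 0.8% | 0% |
| OR 0.5, any coefficient, A | 49% | 28% | 13% |
| OR 0.5, any coefficient, B | 43% | 19% | 8% |
| OR 0.5, RIPC itself, B | 16% | 4% | 1% |
| OR 0.5, RIPC itself, C | 14% | 3% | 1% |

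With a further run (D) of the same kind, the any-coefficient ranges are roughly 2–33% with no effect and 7–49% at an odds ratio of 0.5.

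Exact check for a model with arm alone: RIPC separates when all events fall in one arm, with probability [C(36,e) + C(35,e)]/C(71,e). For e = 5 this is (376,992 + 324,632)/13,019,909 = 5.4%. It is 1.1% for 7 events and 0.09% for 10.

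**Step 3: precision and exaggeration of the RIPC estimate.**
- Root mean squared error of the log odds ratio, no effect, 10–20% risk: maximum likelihood 0.77–1.02, Firth 0.64–0.76. At 35% risk (71 × 0.35 ≈ 25 events): 0.59 against 0.52.
- Geometric-mean odds ratio when the truth is 0.5, 15–20% risk: maximum likelihood 0.41–0.46, Firth 0.48–0.53.

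**Step 4: test size at nominal 5%.**
- In the five-covariate runs the likelihood-ratio test rejected in about 7–9% under no effect. Separate simulations with the number of events fixed gave 6.8–8.7% at 10–14 events with four to six mixed covariates, and 5.6–6.9% when all covariates were binary.
- Wald: 2.5–5.2% in B and C. With fixed events and mixed covariates (two to eight) it was 0.1–0.4% at 5 events, 1.2–2.0% at 7, 3.5–4.3% at 10 and 4.4–5.9% at 14.
- Firth penalised likelihood-ratio: 3.7–5.8% in the five-covariate runs.

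**Step 5: more events.** At 21–28 events with fixed event counts and two to eight covariates, RIPC separation essentially disappears; Wald is 4.8–5.9% and likelihood-ratio 5.6–7.9%.

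**The case against.** The strongest reply is that the decisive inputs are not in the documents. No CIN rate is stated, no covariates are listed or counted, and maximum likelihood is inferred from an unqualified method name. Section 1 explains why earlier trials may disagree; it does not propose model terms. All of this stands, and it is why the figures are conditional ranges. It does not remove the point: the word covariates is plural, the unqualified name ordinarily means maximum likelihood, and nothing in the documents assures 20 or more events.

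A second reply is that section 7.4 is not designated the primary analysis and the chi-square test in section 7.2 does not depend on it. That also stands. A reader might infer that a failed model leaves the primary endpoint without an answer; it does not.

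Two stronger readings should be resisted. One is that the adjusted RIPC estimate will often not exist. The large percentages count any coefficient; RIPC itself was affected in about 0–5% of trials with no effect and 1–16% at an odds ratio of 0.5. It becomes common without an effect only in corners such as 5 events with six or eight covariates (15.9–33.4%). The other is that the test of RIPC rejects too often. That holds for the likelihood-ratio test, and modestly; the Wald test is conservative or near nominal, and its cost is lost power. Nor do the documents show that covariates were dropped to obtain convergence.

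Finally, restricting the model to one or two covariates, or fitting predictors singly, would be a preference: Firth held its size with all five covariates.

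**Conclusion.** The point holds as a weakness of the adjusted analysis and the predictor analysis, and is worth correcting because the correction is cheap. If CIN risk is 10–20% and about five covariates enter, the fit fails for at least one coefficient in anything from a few per cent to nearly half of trials, depending on risk and true effect. The RIPC odds ratio is less precise than it need be, and a true odds ratio of 0.5 is reported on average as about 0.41–0.46. The likelihood-ratio and Wald tests err in opposite directions when events are scarcest. Listing the covariates would not by itself cure this.

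The conclusion rests on the assumed risk, covariate mix and estimator. Rarer or strongly correlated binary covariates would make separation more frequent; more than about 20 events would largely remove it, although Firth was no less precise there. It does not extend to the unadjusted chi-square comparison.

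**What to change.** Replace section 7.4 with text along these lines: *CIN will be analysed by Firth penalised-likelihood logistic regression, with a profile penalised-likelihood 95% confidence interval and test for the RIPC odds ratio. The model contains randomised arm, baseline creatinine and a short named list of covariates measured before randomisation. This list is fixed and will not be changed in response to convergence or results. Analyses of predictors use the same method and are exploratory. This specification was adopted after the CIN comparison between arms had been examined, and is reported as post hoc.*

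Baseline creatinine adds no data collection, because the endpoint definition in section 6 already requires it. Section 7.9 should name the software used for the Firth fit.

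The cost is one SAP paragraph, a Firth routine outside base SPSS (R, for example), slight shrinkage of the odds ratio towards 1, and the discipline of a short covariate list. The post hoc label is unavoidable given section 9.

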## 7.5 Assumption Verification

Assumption	Test Used
Normality	Shapiro-Wilk
Equal variances	Levene

## 7.6 Missing Data

- $\leq 5\%$  Complete case.
- $\geq 5\%$ : Multiple imputation considered
- Sensitivity analysis may be performed

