## 6. Outcome Measures

### **Primary Endpoint**

- CIN defined as either a 25% increase in serum creatinine (SCr) from baseline or a 0.5 mg/dL increase in absolute SCr value—within 72 hours after intravenous contrast administration.

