## 7.3 Repeated Measures

- **Two-factor ANOVA with repeated measures** under General Linear Model (GLM).
- **Post hoc tests:** Bonferroni or Tukey, depending on variance structure.

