## 7.8 Analysis Populations

- **Intention-to-Treat (ITT)**
- **Per Protocol (PP)**  
Both populations will be analyzed and compared

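### The 5% complete-case rule has no stated unit and no mandatory sensitivity analysis, so it can remove randomised patients from analyses labelled ITT and need not cap the loss at 5% in the multi-input models

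*Combined protocol and SAP*

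**What the plan says.** Section 7.6 is the whole missing-data plan. At or below 5% missing the handling is "Complete case". At or above 5% the text is "Multiple imputation considered", which is not a commitment. The third line is "Sensitivity analysis may be performed", with no content given. The section does not say what the 5% is a percentage of.

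Sections 3 and 7.8 name ITT and per-protocol populations. Section 7.8 adds "Both populations will be analyzed and compared". Neither section defines ITT or says what happens to a randomised patient whose outcome is missing.

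Three analyses are affected:

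- **CIN, the primary endpoint (section 6).** It is a rise in serum creatinine from baseline, assessed "within 72 hours after intravenous contrast administration", so it needs a baseline value and at least one later value. Section 7.2 compares qualitative variables by chi-square.
- **Repeated measurements (section 7.3).** The method is "Two-factor ANOVA with repeated measures" under the general linear model. The number of time points is not given.
- **Adjusted CIN model (section 7.4).** This is a binary logistic regression "adjusted for covariates". The covariates are neither named nor counted.

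Section 9 reports that "only 71 patients were enrolled".

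**The concern.** Complete-case analysis deletes patients. If a randomised patient without a CIN status is left out, the result no longer covers everyone randomised, whatever its label. Missing post-contrast creatinine may plausibly be related to early death, transfer or discharge, and so to outcome. In a trial of 71 patients a few such cases matter, and the plan requires nothing that would show how much.

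The second issue is how deletion accumulates. Conventional repeated-measures ANOVA drops a patient who lacks any one time point, and logistic regression drops a patient who lacks any one covariate. If the 5% is counted variable by variable, every variable can satisfy the rule while the model loses more than 5% of its rows. The biomarker and adjusted results would then rest on a smaller and possibly selected set of patients, and partial biomarker data would be discarded.

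**Working it through.** The documents give no expected missing rate, dropout rate or complete-case loss, so there is no figure of the plan's own to reproduce.

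**Inputs from the documents.** N = 71 (section 9); threshold 5% (section 7.6).

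**Assumed inputs, not in the documents.** About 35 patients per arm; k = 4 or 5 incomplete inputs (time points or covariates) per model; 1%, 2% or 3/71 missing on each.

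**Step 1. Most patients one variable can lose under the rule.** 0.05 × 71 = 3.55, so 3 patients: 3/71 = 4.2%. A fourth would give 4/71 = 5.6%, which is above the threshold.

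**Step 2. Primary endpoint.** If all 3 missing CIN outcomes fall in one arm of 35, that arm's risk over all its randomised patients can vary by 3/35 = 8.6 percentage points, according to whether none or all of the 3 had CIN. A split between the arms gives a smaller range in each.

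**Step 3. Models that need complete rows, threshold read per variable.** With a fraction r missing on each of k inputs, independently, the share of patients lost is 1 − (1 − r)^k.

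| Missing per input | k = 4 | k = 5 |
|---|---|---|
| 1% | 1 − 0.99^4 = 3.9% | 1 − 0.99^5 = 4.9% |
| 2% | 1 − 0.98^4 = 7.8% | 1 − 0.98^5 = 9.6% |
| 3/71 (the ceiling) | 1 − (68/71)^4 = 15.9%, about 11 patients | 1 − (68/71)^5 = 19.4%, about 14 patients |

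**Step 4. Where the loss stays small.**

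- If the same 3 patients are missing on every input (full overlap), the loss is 3/71 = 4.2% for any k.
- If the 5% applies to rows lost per model, or to the whole analysis set, the complete-case branch allows at most 3 patients, again 4.2%. A larger loss moves to the imputation branch.
- The unadjusted chi-square on CIN, taking CIN status as one variable, also loses at most 3.

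**The case against.** The strongest reply is that the rule may be harmless. Section 7.6 never says the 5% is per variable. Read per model, it caps the complete-case loss at 3 patients. Even on the per-variable reading, the likely causes of missingness act on the whole patient: someone who dies or leaves early loses all later samples together. That contradicts independence and pulls the loss towards 4.2%. This stands. What remains is that a threshold with no stated unit does not by itself bound the loss.

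Two stronger readings are tempting, and the documents support neither.

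- A reader might infer that 15–20% of patients will be lost. That needs a per-variable threshold, 4–5 incomplete inputs each near the 3-patient ceiling, and roughly independent missingness. The plan states none of these.
- A reader might infer that deletion could overturn the primary result. Counts can be invented to suggest it. With 2/32 against 8/36, the uncorrected Pearson p-value is 0.063; if the 3 omitted patients had no CIN, 2/35 against 8/36 gives 0.046. Fisher's exact test on the same tables gives 0.089 and 0.085, so the crossing of 0.05 depends on the choice of test as well as on invented counts. Section 9 reports no significant CIN difference and gives no event counts, so nothing shows that deletion affected the conclusion.

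It is also fair to say that imputing at most 3 CIN outcomes is a matter of preference. Best-case and worst-case bounds serve the purpose.

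**Conclusion.** The concern holds in a limited form. Followed as written, section 7.6 removes randomised patients from analyses called ITT, and no sensitivity analysis is required to show the effect.

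For CIN the loss under the complete-case branch is at most 3 of 71. That is 8.6 percentage points of uncertainty in one arm's risk if all 3 are in an arm of about 35, and the arm size is an assumption. The compounding in step 3 does not reach the unadjusted CIN comparison.

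For the repeated-measures and adjusted models the loss can exceed 5%, but only on the per-variable reading. The range of roughly 4% to 19% is a scenario, not a forecast: the number of inputs, the missing rates and independence are all assumed. The effect on planned power cannot be computed, because section 3 sets the sample by convenience over a fixed period and gives no power basis.

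**What to change.** Revise sections 7.3, 7.4, 7.6 and 7.8 as follows.

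- **Repeated biomarkers.** Replace the general linear model ANOVA with a linear mixed model fitted to all available time points, so that a patient with one missing sample still contributes the others.
- **CIN.** Define ITT as all randomised patients. Always report best-case and worst-case results for missing CIN, whatever the percentage missing.
- **Adjusted model and threshold.** Apply the 5% to the rows lost per model. Impute missing baseline covariates rather than deleting the patient. Report the N used in each model, by arm.

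Section 9 shows that the data have already been analysed, so these changes should be disclosed as post hoc. No new patients or measurements are needed. The cost is modest extra analysis and possibly slightly wider intervals.

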## 7.7 Multiple Comparisons

- Bonferroni or False Discovery Rate (FDR) correction applied where appropriate

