### **Secondary Endpoints**

- Plasma, urinary, and intracellular HO-1 levels.
- Oxidative stress markers (MDA).
- Cardiac stress biomarkers (NT-proBNP).
- Inflammatory and hematological indices: C-reactive protein (CRP), Total leukocyte count, Neutrophil and lymphocyte counts Neutrophil-to-lymphocyte ratio (NLR).
- Duration of ICU/hospital stay duration
- Mortality, readmission, clinical status and need for dialysis.

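### Where familywise control is applied across secondary endpoints, Holm's step-down procedure should replace the single-step Bonferroni correction named in section 7.7

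*Combined protocol and SAP*

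**What the plan says.** Section 7.7 of the SAP gives one line on multiplicity: "Bonferroni or False Discovery Rate (FDR) correction applied where appropriate". It offers two routes, one controlling the familywise error rate and one controlling the false discovery rate. It does not say which route applies to which endpoints, and it defines no family of tests.

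The secondary endpoints in section 6 begin with "Plasma, urinary, and intracellular HO-1 levels", which is three measures, followed by MDA, NT-proBNP, five inflammatory or haematological indices, length of stay and clinical outcomes. By count that is 3 + 1 + 1 + 5 = 10 biomarkers.

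Section 7.10 states "All tests two-sided", with p < 0.05 "considered statistically significant". Section 7.3 has a separate rule for post hoc tests within the repeated-measures model, "Bonferroni or Tukey, depending on variance structure". That rule is outside this point. Section 3 gives the sample: "Actual enrolled patients: 71".

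**The concern.** Single-step Bonferroni compares every p-value with 0.05/m. Holm compares the smallest with 0.05/m, the next with 0.05/(m − 1), and so on up to 0.05, stopping at the first failure. Both hold the familywise error at 5% or less whatever the correlation between tests. Because no Holm threshold is below 0.05/m, Holm rejects every hypothesis that Bonferroni rejects and sometimes more. For testing alone, Bonferroni therefore gives up sensitivity without gaining any error control.

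This bears on the first secondary objective (section 2), which concerns HO-1 and oxidative stress. HO-1 is measured in three compartments alongside MDA, and section 9 itself cites reduced power with 71 patients. If several of these markers respond, that is the setting in which the step-down thresholds help most.

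**Working it through.** The plan states no adjusted alpha, family size, biomarker effect size or biomarker power, so there is no figure of its own to reproduce. What follows is an illustration on stated assumptions.

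**Inputs from the documents.** Two-sided alpha 0.05 (7.10); three HO-1 measures and MDA, within ten biomarkers in all (section 6); 71 patients (section 3).

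**Assumptions.** Each truly changed marker has 80% power at unadjusted 0.05. The test statistics are normal. Family sizes are m = 3 (HO-1 only), 4 (HO-1 plus MDA), 10 (all biomarkers) and 16 (a wide set of secondary endpoints). Correlation between tests is 0, or 0.5 where stated.

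**Step 1: noncentrality.** 80% power at two-sided 0.05 needs a mean test statistic of 1.960 + 0.842 = 2.80. If the arms were 35 and 36 (the split is not given), this is a standardized difference of 2.80 × √(1/35 + 1/36) = 2.80 × 0.237 ≈ 0.67.

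**Step 2: Bonferroni power per marker.** Power ≈ Φ(2.80 − z), where z is the two-sided critical value at 0.05/m.

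| m | 0.05/m | z | Power |
|---|---|---|---|
| 3 | 0.0167 | 2.394 | 66% |
| 4 | 0.0125 | 2.498 | 62% |
| 10 | 0.0050 | 2.807 | 50% |
| 16 | 0.0031 | 2.955 | 44% |

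**Step 3: Holm power per marker.** This was obtained by simulation (at least 100,000 runs per scenario for the 3-, 4- and 16-test families with all or four true effects) and averaged over the truly changed markers.

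| Family | True effects | Correlation | Bonferroni | Holm | Gain (points) |
|---|---|---|---|---|---|
| 3 | 3 | 0 | 65.8% | 75.0% | 9 |
| 3 | 3 | 0.5 | 65.9% | 73.6% | 8 |
| 4 | 4 | 0 | 61.9% | 72.7% | 11 |
| 4 | 4 | 0.5 | 61.9% | 71.0% | 9 |
| 4 | 3 | 0 | 62% | 68% | 6 |
| 4 | 2 | 0 | 62.1% | 64.6% | 2.5 |
| 4 | 1 | 0 | 61.8% | 61.9% | 0.1 |
| 10 | 4 | 0 | 49.8% | 52.1% | 2 |
| 16 | 4 | 0 | 43.8% | 44.9% | 1 |

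No run contained a Bonferroni rejection that Holm missed. In the four-marker scenarios with some true nulls, Holm's simulated familywise error was at most 4.4%.

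**Step 4: what does not change.** The first Holm threshold equals Bonferroni's, so the chance of rejecting anything at all is the same under both. When every tested marker truly changes, this means the chance of at least one detection is unchanged. What improves is the number of markers confirmed. With all four changed, the chance of confirming all four rises from 15% to 38% (32% to 53% at correlation 0.5).

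**Step 5: a check from fixed effect sizes.** Take arms of 35 and 36 and independent tests. With m = 10 and five true effects, power moves from 24.1% to 25.2% at a standardized difference of 0.5, and from 71.4% to 75.3% at 0.8. With all ten true it moves from 24.2% to 27.4% and from 71.3% to 85.8%. With m = 3, all true, it moves from 38.7% to 45.0% and from 83.8% to 90.1%. The pattern is the same: the gain is small when few markers respond and material when most do.

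**The case against.** Bonferroni is a valid procedure, so no error has been found, and the same remark could be made of any plan that names it. Validity is granted; the point rests on efficiency alone. A method that controls the same error, never rejects less and needs only sorted p-values is still worth adopting.

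Section 7.7 also allows FDR, and the usual Benjamini-Hochberg procedure rejects at least as often as Holm (77% against 73% in the four-marker, all-true case). That is correct, but it controls a different error rate. With 16 endpoints and four true effects, the chance of at least one false rejection was about 12% under Benjamini-Hochberg and 4% under Holm. The FDR option therefore does not make the choice of familywise method irrelevant.

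The larger gains need a small family in which every marker responds. The plan defines no such family, and section 1 warns that diabetes may blunt these very pathways. This stands: the 9 to 11 points are the favourable end of the range. Correlation between markers also lowers the average gain slightly.

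Replacing Bonferroni with Holm leaves open when a correction applies and to which tests. That stands too, as a separate weakness that this change does not repair.

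A reader might infer that the plan causes real biomarker effects to be lost. The documents do not support that. They do not assign Bonferroni to HO-1 or MDA, and they report no biomarker result that a different correction would alter.

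**Conclusion.** The point holds as a low-severity efficiency improvement. Where 7.7 is read as familywise control across secondary endpoints, single-step Bonferroni is dominated by Holm for hypothesis testing. That dominance needs no assumption about correlation or effect size.

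The size of the gain does depend on assumptions. The 80% unadjusted power, the family sizes and the correlations are illustrative and do not come from the plan. Across the 80%-power scenarios the gain in average power per marker runs from about 0.1 point (one true effect among four) to about 11 points (all four true). It is about 1 to 2 points in a family of 10 to 16 with four true effects. The CIN primary endpoint, tested on its own, is untouched.

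**What to change.** In section 7.7, replace Bonferroni with Holm step-down Bonferroni for familywise control across secondary endpoints, and leave the FDR option as it is. The post hoc rule in 7.3 need not change for this point.

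The cost is small. No data or patients are needed, and the adjusted p-values come from sorting the unadjusted ones. Simultaneous confidence intervals are less simple under Holm than under Bonferroni, but the plan does not specify any.

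Section 9 says that data collection ended in January 2017 and that preliminary analyses were done, so this would be a late move to a less conservative rule. It should be dated and disclosed as such, with the Bonferroni results reported alongside so that readers can see whether any conclusion depends on the change.
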